8.2 Definition of Analyses Populations

Enrolled population: All participants enrolled.

Full Analysis Set (FAS) / A Safety population

All eligible participants treated with cabozantinib within this

non-interventional study.

8.2.1 Populations Analysed

The primary and secondary effectiveness analyses will be based on the FAS population.

8.2.2 Participant Allocation and Reasons for Exclusion from the Analyses

The rules for the allocation of participants to each of the analysis populations will be defined and documented during a data review meeting held prior to database lock.

During the data review meeting, based on minor or major protocol deviations recorded, participants may be excluded from the safety/FAS population.

8.3 Sample Size Determination

As this is a non-confirmatory, exploratory, non-interventional study, no formal sample size calculation was performed.

Based on the feasibility evaluation, it was estimated that 150 participants in approximately 50 sites could be enrolled in this study. No power calculations have been performed since this is a non-interventional study with a descriptive objective.

Assuming a dropout rate of 10%, 135 participants will be evaluable for the primary endpoint (DCR). With a sample size of 135 participants, a two-sided 95% CI for a sample proportion using the normal approximation will extend to $\pm 7.5\%$ from the observed proportion for an expected DCR of 73% (145/198), based on the Cabinet study [14] with both pNET (51/64) and epNET (94/134) cohorts pooled.

PAGE 34/52

8.4 Statistical and Analytical Methods

Statistical analyses will be performed using Statistical Analysis System (SAS)[®] (Version 9.4 or higher).

As this is a non-interventional study, no formal statistical testing will be performed, and all the analyses will be primarily descriptive in nature. When appropriate and unless otherwise specified, two-sided 95% CIs will be displayed. If p-values are presented, this will be for exploratory purposes only.

Descriptive statistics will include number of available data, number of missing data and the following:

- Mean, Standard Deviation (StD), minimum, median, maximum, first and third quartiles and 95% CIs for means;
- Counts and percentages of each category for categorical nominal variables with 95% CIs. Percentages will be based on the number of non-missing observations.

Missing data will not be replaced. Imputation rules will be detailed in the SAP, as appropriate (e.g. for incomplete dates).

8.4.1 Demographic and Other Baseline Characteristics

Descriptive summary statistics of demographic and baseline data (including NET medical history, characteristics of NET at start of cabozantinib, NET-specific concomitant medication and previously received therapies for NET) will be presented for the FAS population.

8.4.2 Participant Disposition and Withdrawals

The numbers and percentages of participants in the FAS population will be tabulated by country and centre. The reasons for participant exclusions from each of the populations will also be tabulated. In addition, the number of participants who were treated and withdrawn will be tabulated. Primary reasons for withdrawal from the study will be tabulated.

8.4.3 Effectiveness Analysis

8.4.3.1 Primary Effectiveness Analysis

The primary endpoint is the DCR at 6 months, defined as the proportion of participants who, within 6 months achieve CR, PR or SD determined based on radiographic assessments between the date of the first dose of cabozantinib until the date of progressive disease (PD) or date of subsequent therapy.

The proportion of participants with DCR will be calculated by counting all participants who have SD, PR or CR at any post-baseline TA and dividing them by the number of participants in the FAS with at least one post-baseline TA. Participants who are treated with cabozantinib beyond progression but have not had SD, PR or CR prior to disease progression, will be considered to have no SD, PR or CR, even if they achieve SD, PR or CR after PD. DCR will be provided with the corresponding 95% CI.

In a secondary analysis, the DCR will be calculated similarly except that the count of participants who have SD, PR or CR at any post-baseline TA will be divided by the number of participants in the FAS.

PROTOCOL FINAL V1.0: 30 JULY 2025

PAGE 35/52

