4.1 Overview

This is an international, multicentre, non-interventional, prospective, single-arm study. This study will be conducted in up to 50 centres in Austria and Germany. A total of 150 participants will be included in the study. Participants will be treated and monitored in accordance with usual medical practice during their participation in this study.

The expected duration of the recruitment period will be 18 months. Participants will be followed for a maximum of 18 months (observation period) while they receive cabozantinib as per the SmPC.

Participants prematurely discontinuing cabozantinib (i.e. within the first 15 months of observation period) and initiating a subsequent treatment will be followed up approximately 3 months after the treatment switch to collect effectiveness data for the new LoT. Enrolment in the study is possible if cabozantinib treatment started up to 4 weeks prior to enrolment. The data for Visit 1 will be captured retrospectively and starting at Visit 2 data will be collected prospectively including hrQoL baseline assessment.

To avoid selection bias in participant recruitment, investigators will offer enrolment to all eligible participants consecutively to achieve their recruitment target during a restricted and defined period. This includes patients who have stopped cabozantinib treatment within their first 4 weeks to avoid selection bias. But, if consecutive enrolment is not feasible (e.g. administrative constraints), an alternate enrolment schedule will be permitted and will have to be documented before the first participant is enrolled. The investigators will have to follow the same recruitment pace until achievement of his/her recruitment target.

4.2 **Population Characteristics**

One hundred and fifty (150) adult participants with unresectable or metastatic, well -differentiated epNET and pNET who have progressed following at least one prior systemic therapy other than SSA, and who are prescribed cabozantinib tablets according to the SmPC prior to entry into the study will be included in Austria and Germany.

Further details of the study population are provided in Section 5.

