8.5 Subgroup Analyses

Subgroup analyses are only performed if data permit. Subgroups may be merged into larger subgroups if deemed necessary. The following subgroups are defined:

Subgroups NET localisation:

NET-I LungNET (27.3%)
NET-II GI-NET (53.2%)
NET-III pNET (7.3%)
NET-IV Other NET (12.2%)

Estimation for subgroup sample size: The breakdown into subgroups follows the distribution described in the literature for NET [4,6]. Due to the difference in treatment sites for LungNET and other NETs in Germany and Austria the LungNET cohort is estimated to be approx. 20% and the other NETs make up approx. 80% of the sample size. All endpoints will be analysed for the subgroups if participant collective allows it.

Feasibility of subgroup assessment will be completed following the enrolment of all participants in this study. If necessary, these subgroups may be combined to make larger groups.

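### The primary DCR (and ORR) counts only participants with a post-baseline tumour assessment, so deaths and early stops before any assessment leave the denominator; the full-FAS version should be primary

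*Protocol*

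**What the plan says.** - Protocol 8.2 defines the FAS as "All eligible participants treated with cabozantinib within this" study. No tumour assessment is required for membership. Section 8.2.1 adds: "The primary and secondary effectiveness analyses will be based on the FAS population".
- Protocol 8.4.3.1 forms the primary DCR by counting participants with SD, PR or CR and "dividing them by the number of participants in the FAS with at least one post-baseline TA". Its last paragraph keeps the numerator for a secondary analysis in which the count "will be divided by the number of participants in the FAS". Section 8.4.3.2 uses the same pair of denominators for ORR and analyses next-line DCR in the same way as the primary endpoint.
- Protocol 8.4 bases percentages on non-missing observations and does not replace missing data. Nothing in the primary analysis counts a participant without a TA as a failure.
- Table 4-1 shows no TA at Months 1 and 2; after baseline the first is at Month 3. Section 4.5 expects imaging about every 3 months.
- Protocol 4.1, on recruitment, says of consecutive enrolment: "This includes patients who have stopped cabozantinib treatment within their first 4 weeks to avoid selection bias".
- Protocol 8.3 assumes 10% dropout from 150, leaving 135 evaluable for DCR, and gives ±7.5% around an expected 73%.

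**The concern.** Having a post-baseline TA is something that happens, or fails to happen, after treatment starts. Someone who dies in week 6, or stops for toxicity in week 3 and is not assessed again, has not been shown to have disease control, yet is removed from the primary rate instead of being counted against it. Such losses tend to go with poor outcome, so the headline DCR moves upward.

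Early stops are realistic on the protocol's own evidence: section 2.3 reports treatment durations in the cited phase III trial down to 0.5 months (pNET) and 0.2 months (epNET). Section 4.1 takes care to bring early stoppers into the study, and the primary formula can then take the same people out of its main result. At stake is a shift in the main descriptive estimate of about the size of its planned confidence interval half-width, in the direction favourable to the product.

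**Working it through.** **Inputs, all from protocol 8.3:** N = 150; 10% non-evaluable; expected DCR 73% (145/198); two-sided 95% interval by normal approximation.

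**Step 1. Reproduce the plan's figures.**
- Evaluable: 150 × (1 − 0.10) = 135.
- Pooled rate: (51 + 94)/(64 + 134) = 145/198 = 73.2%.
- Half-width: 1.96 × √(0.73 × 0.27/135) = 7.49 points. The stated ±7.5% is confirmed.

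**Step 2. Gap between the two denominators.** Let m be the share of the FAS without a post-baseline TA. The numerator is common, so DCR(FAS) = DCR(assessed) × (1 − m). With m = 10%:
- If 73% is the rate among the 135 assessed, the full-FAS rate is 0.73 × 0.90 = 65.7%, a gap of 7.3 points. In whole participants: 99/135 = 73.3% against 99/150 = 66.0%.
- If 73% is the rate over all 150, the assessed-only rate is 0.73/0.90 = 81.1%, a gap of 8.1 points. In whole participants: 110/135 = 81.5% against 110/150 = 73.3%.

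**Step 3. How much of the gap is bias.** Let q be the true DCR among those without a TA, with 73% among the assessed. The true overall rate is 0.73 × 0.90 + 0.10 × q, so the overstatement is 0.10 × (0.73 − q).

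| q | True overall DCR | Overstatement |
|---|---|---|
| 0% | 65.7% | 7.3 points |
| 25% | 68.2% | 4.8 points |
| 50% | 70.7% | 2.3 points |
| 73% | 73.0% | 0 points |

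**Step 4. Other values of m (assumed), all non-assessed non-controlled.** The first gap is 0.73 × m; the second is 0.73/(1 − m) − 0.73.

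| m | 73% among assessed | 73% over full FAS |
|---|---|---|
| 5% | 3.7 points | 3.8 points |
| 10% | 7.3 points | 8.1 points |
| 15% | 11.0 points | 12.9 points |
| 20% | 14.6 points | 18.3 points |

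**Step 5. Precision with the full FAS, n = 150.**
- At 73%: 1.96 × √(0.73 × 0.27/150) = 7.1 points.
- At 65.7%: 1.96 × √(0.657 × 0.343/150) = 7.6 points.

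**The case against.** The strongest reply is that the full-FAS rate is already pre-specified for both DCR and ORR. The study is descriptive, no formal test depends on the label, and a reader of the report will see both figures. The primary denominator is a subset of the FAS, so it does not contradict section 8.2.1, and it follows the general rule in 8.4 on non-missing observations. Early stoppers also still count in the safety analysis and in Kaplan-Meier PFS. All of this stands. What remains is that the figure designated primary, and the one on which 8.3 bases its precision, is the one conditioned on being assessed.

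Several stronger readings are tempting and are not supported:

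- *Early clinical progressions also vanish.* Footnote d of Table 4-1 defines a TA as clinical and/or by imaging, and the PD definition includes progression indicated by the clinician. A recorded clinical progression can therefore keep the participant in the denominator as non-controlled. It drops out only if TA in 8.4.3.1 means a radiographic TA. That section bases response on radiographic assessment but does not say which kind of TA the denominator needs.
- *Every toxicity stop is lost.* A TA is also listed at the follow-up visit, and section 4.5 lists TA generally for Visits 2 to 9, so some early stoppers will have one. The rescue is partial: footnote b ties the follow-up visit to a therapy switch, and the endpoint window closes at subsequent therapy.
- *Missing TAs are all failures.* Section 8.3 calls the 10% dropout, and section 4.3 allows assessments that are not routine at a site to go unrecorded.
- *The planning benchmark used a different denominator.* Section 8.3 describes the 73% as "with both pNET (51/64) and epNET (94/134) cohorts pooled" but does not say whether those totals are randomised, treated or assessed patients. The point cannot be settled here.
- *The tumour mix behind 73% is wrong for this study.* That is a separate matter. The pNET share in 8.5 is a literature figure, and the same section then adjusts the expected mix.

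**Conclusion.** The point holds for participants who die, or who stop and are not assessed, before any TA: they leave the primary DCR and ORR, and the effect is upward whenever they do worse than those assessed. At the protocol's own 10%, the gap between the two versions is 7.3 to 8.1 points, against a planned half-width of 7.5.

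That size is a scenario and not a limit. It assumes that exactly 10% lack a TA and that none of them had disease control. It shrinks to zero if they did as well as the rest, and grows if more than 10% lack a TA. A reader might infer that 8 points is the most the DCR can be inflated, or that the result will certainly be inflated by that much; the protocol supports neither. Because both versions are planned, the defect lies in which one is primary and in the undefined TA, not in a missing analysis.

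**What to change.** 1. In 8.4.3.1, make the full-FAS DCR primary, with no post-baseline TA counted as not controlled. Keep the assessed-only DCR as supportive, with reasons for a missing TA tabulated (death, clinical progression, treatment stop, therapy switch, scan not done).
2. State whether a clinical TA counts as a post-baseline TA.
3. Make the same change for ORR and for next-line DCR in 8.4.3.2; for the latter, the denominator becomes all FAS participants who switched.
4. Restate the precision in 8.3 and the synopsis for n = 150: ±7.1 points if 73% is taken as the full-FAS rate, or about ±7.6 if 73% is the assessed-only rate and the full-FAS rate is 65.7%. Say which is meant.

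The cost is wording only; both analyses are already planned and no new data are needed. The change is best made before the second interim analysis, the first to report effectiveness. The downside is a lower reported DCR, with scans missing for administrative reasons counted as failures. The supportive analysis and the table of reasons will show how much that matters.

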8.4.3.2 Secondary Effectiveness Analysis

Objective response rate (ORR):

ORR is defined as the proportion of participants who achieve CR or PR determined based on radiographic assessments between the date of the first dose of cabozantinib and the date of PD or date of subsequent therapy.

The proportion of participants with ORR will be calculated by counting all participants who have PR or CR at any post-baseline TA and dividing them by the number of participants in the FAS with at least one post-baseline TA. Patients who are treated with cabozantinib beyond progression but have not had PR or CR prior to disease progression, will be considered to have no PR or CR, even if they achieve PR or CR after PD. ORR will be provided with the corresponding 95% CI.

In a secondary analysis, the ORR will be calculated similarly except that the count of participants who have PR or CR at any post-baseline TA will be divided by the number of participants in the FAS.

QLQ-C30 global and subscale scores for each visit at which hrQoL was assessed:

See Section 8.4.5.

QLQ-GINET21 subscale scores for each visit at which hrQoL was assessed:

See Section 8.4.5.

Duration of treatment (DoT) and time to next treatment (TTNT):

Both DoT and TTNT will be presented descriptively as quantitative parameters. TTNT will be presented for the subgroup of participants with a subsequent therapy.

Progression-free survival:

PFS will be estimated on the FAS, using the Kaplan-Meier method and plotted as a survival curve.

The survival rates at 12-month follow-up and 18-month follow-up will be estimated and presented with their 95% CIs.

If the number of events allows, the median PFS, first and third quartiles with their two-sided 95% CIs will be presented.

Biomarker assessments:

CgA levels at each visit where CgA was assessed will be summarised for each visit by descriptive statistics providing n, mean, 95% CI of the mean, StD, median, minimum, and maximum. NSE levels at each visit where NSE was assessed will be summarised for each visit by descriptive statistics providing n, mean, 95% CI of the mean, StD, median, minimum, and maximum.

Switch to subsequent therapy:

The proportion of participants who permanently discontinued cabozantinib and started a new LoT will be described, as well as the types of therapies in this subsequent line.

The DCR at 3 months after the switch to the next LoT will be analysed similarly to the primary endpoint, except that the population of analysis will be the FAS for participants who switched to the next LoT.

PAGE 36/52

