	• To describe the potential impact of cabozantinib treatment on NET biomarkers.							
	• To describe the time to next treatment (TTNT) for cabozantinib.							
	• To describe the progression free survival (PFS).							
	Exploratory objectives							
	To describe supporting measures.							
	• To describe potential correlations between effectiveness outcomes or quality of life and occurrence of AEs, dose reduction or supportive measures.							
Rationale	Neuroendocrine tumours (NETs) are rare, heterogeneous neoplasms originating from cells of the diffuse neuroendocrine system. They can arise in various organs, most commonly in the gastrointestinal tract, pancreas, and lungs. Based on differentiation and proliferation rate, NETs are classified into grades 1 to 3, with grade 3 tumours showing higher proliferative activity. Gastroenteropancreatic NETs (GEP-NETs) account for the majority of cases, while lung-NETs are the most frequent non-GEP-NETs. Treatment strategies vary depending on tumour location, grade, and other clinical factors, and include somatostatin analogues, targeted therapies, peptide receptor radionuclide therapy (PRRT), and chemotherapy. Cabozantinib is a multi-tyrosine kinase inhibitor targeting mesenchymal-epithelial transition							

factor (c-MET), vascular endothelial growth factor receptor kinases involved in tumour progression. It has been approved in the European Union (EU) for several indications, including renal cell carcinoma, hepatocellular carcinoma, and differentiated thyroid carcinoma. In 2025, cabozantinib received EU approval for the treatment of unresectable or metastatic, well differentiated pancreatic (pNET) and extra-pancreatic NET (epNET) who have progressed following at least one prior systemic therapy other than somatostatin analogues. In the phase III CABINET trial, cabozantinib significantly prolonged progression-free survival (PFS) compared to placebo in patients with advanced, well-differentiated pNET and epNET, with median PFS of 13.8 and 8.4 months, respectively. This non-interventional study aims to evaluate the real-world effectiveness and safety of cabozantinib in patients with NETs. It will also assess the impact of dose modifications on treatment duration, explore quality of life outcomes, and collect data on prior and subsequent therapies.

Study Timelines

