3 OBJECTIVES AND ENDPOINTS

	Objectives	Endpoints			
Prima	ary				
•	To describe the effectiveness of cabozantinib tablets in participants with previously treated neuroendocrine tumours (NETs) in real-life in terms of disease control rate (DCR) at 6 months of cabozantinib treatment as assessed by the treating physician.	• The primary endpoint is the DCR defined as proportion of participants who within 6 months achieve complete response (CR), partial response (PR) or stable disease (SD) determined based on radiographic assessments between the date of the first dose of cabozantinib until the date of progressive disease (PD) or date of subsequent therapy.			
Secon	ndary				
•	To describe the objective response rate (ORR) as investigated by the treating physician.	 ORR defined as proportion of participants who achieve CR or PR determined based on radiographic assessments between the date of the first dose of cabozantinib and the date of PD or date of subsequent therapy. 			
•	To describe health-related quality of life (hrQoL) over the course of cabozantinib treatment.	 QLQ-C30 global and subscale scores for each visit at which hrQoL was assessed. QLQ-GINET21 subscale scores for each visit at which hrQoL was assessed for GI-NET participants. 			
•	To describe the safety of cabozantinib by review of all nonserious, drug-related and serious adverse events (AEs).	 All AEs assessed according to incidence, intensity/grade, causality, outcome, action taken and seriousness, specifically: a) Frequency of serious AEs (SAEs). b) Frequency of drug-related non serious AEs (nsAEs). c) Frequency of drug-related SAEs. 			

	Objectives	Endpoints				
•	To describe cabozantinib dosage adjustment and schedule.	 All dose modifications according to frequency, timing, reason for adjust- ment, type of adjustment and duration of modified dosing, specifically: 				
		(a) Frequency of dose reductions due to AEs.				
		(b) Frequency of dose interruptions due to AEs.				
		(c) Frequency of treatment discontinuations due to AEs.				
	To describe the duration of treatment (DoT) with cabozantinib.	 DoT during cabozantinib treatment phase, defined as the time from first dose until last dose of cabozantinib. 				
•	To describe subsequent therapies following cabozantinib.	 Frequency overall and by type of therapy switch. 				

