4.7 Study Duration/Observation Period

The expected study duration is 3 years, with an 18-month enrolment period from first participant, first visit. The EoS is expected to be a maximum 18 months after the last participant has been enrolled.

The study will be considered to have started when the first participant has signed informed consent.

The study will be considered to have ended after the last participant's data has been collected.

The study observation period starts from participants signing the informed consent and continues until Visit 9 (Month 18). Participants discontinuing cabozantinib treatment and starting a new LoT during the first 15 months of cabozantinib treatment are passing over into the follow-up, which is approximately 3 months after discontinuation of cabozantinib.

Participants will be followed until the end of observational period (i.e. a maximum of 18 months after Visit 1) or withdrawal of consent, or death, whichever occurs first.

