8.4.3.3 Exploratory Effectiveness Analysis

Supporting measures:

Frequency and type of supporting measures (e.g. PSP, psycho-oncological support, nutritional advice etc.) will be summarised for each visit by descriptive statistics providing counts and percentages of each category for categorical nominal variables with 95% CIs.

Exploratory correlation analyses:

Details of exploratory correlation analyses assessing the following correlations will be provided in the SAP. The exploratory analyses will mainly focus on the description of:

- DCR and ORR depending on the number and grade of treatment-related AEs (ADRs).
- DCR and ORR depending on the implementation of dose reductions of cabozantinib.
- The evolution of the hrQoL assessed by EORTC QLQ-C30 and additionally QLQ-GINET 21 for GI-NET participants depending on the occurrence of ADRs and dose reductions.
- The DoT and treatment discontinuation due to AEs in regard to supportive measures the participants received.
- The DoT in regard to dose reduction.
- The DoT in regard to hrQoL.

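### TTNT is summarised only in participants who switched, which biases it short, and DoT has no rule for treatment still ongoing at Month 18

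*Protocol*

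**What the plan says.** On DoT and TTNT, Section 8.4.3.2 reads: "Both DoT and TTNT will be presented descriptively as quantitative parameters. TTNT will be presented for the subgroup of participants with a subsequent therapy". The synopsis also promises a descriptive presentation of both. For PFS the same section chooses differently: "PFS will be estimated on the FAS, using the Kaplan-Meier method and plotted as a survival curve".

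Section 3 gives "DoT during cabozantinib treatment phase, defined as the time from first dose until last dose of cabozantinib". Section 6.1.2 ends DoT at permanent discontinuation instead. TTNT runs from the first cabozantinib dose to the first dose of the next therapy.

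On follow-up, Section 4.7 says "Participants will be followed until the end of observational period (i.e. a maximum of 18 months after Visit 1", or until consent is withdrawn or the participant dies, if earlier. Table 4-1 includes a Month 18 end-of-study visit for participants who have not stopped cabozantinib. Post-cabozantinib treatment is collected in that table only at the follow-up visit, which concerns stops in the first 15 months. Section 8.4 says missing data are not replaced.

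**The concern.** Both endpoints are times to an event observed through a limited window, so some values will be censored. The protocol recognises this for PFS but not for DoT or TTNT.

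For TTNT the stated rule keeps only participants whose event fell inside the window. Those who stay longest without needing another therapy are left out, so the summary is short and depends more on the length of the window than on the drug. For DoT the text does not say what value a participant still on treatment contributes, so the reported figure depends on an unstated choice. The output of a descriptive study is its estimates, and these are two named secondary endpoints. At IA2 and IA3 many participants will have less than 18 months of follow-up, so the distortion would be larger if these durations are reported there.

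**Working it through.** The protocol gives no figure for censoring or precision of DoT or TTNT. Its one precision figure, ±7.5 points for DCR, reproduces (1.96 × √(0.73 × 0.27 / 135) = 7.49 points) but does not bear on this point.

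**Inputs.** Window: 18 months (Section 4.7). Median DoT in the earlier phase III trial: 5.5 months epNET, 8.3 months pNET (Section 2.3). Expected median treatment duration in the synopsis, taken from PFS: 8.4 and 13.8 months. No TTNT median is given, so 9 to 18 months is assumed. Times are assumed exponential.

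**Formulas.** With true median m, the share event-free at 18 months is S = 2^(−18/m), and F = 1 − S. The median among events inside the window is m × log2(1/(1 − F/2)). The true mean is m/ln 2; with ongoing cases entered as 18 months it is (m/ln 2) × F.

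**TTNT in switchers only.**

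| Assumed true median | S | Switcher-only median |
|---|---|---|
| 9 | 0.250 | 6.1 |
| 12 | 0.354 | 6.8 |
| 15 | 0.435 | 7.2 |
| 18 | 0.500 | 7.5 |

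For example, m = 12: F = 0.646, 1 − F/2 = 0.677, log2(1/0.677) = 0.563, and 12 × 0.563 = 6.8. When the true median doubles from 9 to 18 months, the reported one rises by 1.4 months.

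This table gives everyone 18 months of observation. A simulation closer to the visit plan ends follow-up 3 months after stopping for stops up to Month 15. It mixes pNET and epNET with a pNET share of 7.3% (Section 8.5) or 64/198 = 32.3% (Section 8.3), sets dropout at 0 or 10%, and assumes a mean gap of 1 month from stop to next therapy. The true median is 6.7–7.3 months with the quoted DoT medians, and the switcher-only median is 5.4–5.8 (17–22% short). With the synopsis expectation it is 9.7–10.8 against 6.5–6.9 (31–38% short).

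**DoT.**

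| True median | Ongoing at 18 months | Median if ongoing dropped | Mean: true → ongoing entered as 18 |
|---|---|---|---|
| 5.5 (epNET) | 10% | 4.7 | 7.9 → 7.1 (−10%) |
| 8.3 (pNET) | 22% | 5.9 | 12.0 → 9.3 (−22%) |
| 8.4 (synopsis, epNET) | 23% | 5.9 | 12.1 → 9.4 (−23%) |
| 13.8 (synopsis, pNET) | 40% | 7.0 | 19.9 → 11.8 (−40%) |

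Entering ongoing cases as 18 months leaves a median below 18 unchanged if nobody drops out. In the mixture simulation it falls about 5–8% if 10% dropout is counted as a stop.

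**Does Kaplan-Meier recover TTNT under the planned visits?** Using DoT median 5.5 months, an exponential gap to next therapy, and censoring 3 months after stopping (stops up to Month 15) or at Month 18:

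| Assumed mean gap | True median | Kaplan-Meier median |
|---|---|---|
| 1 month | 6.6 | 6.7 |
| 3 months | 8.8 | 10.7 |

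The excess arises because the people censored are off cabozantinib and the most likely to start a new therapy soon.

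**The case against.** Several arguments on the other side have force.

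- **The analyses are descriptive and openly labelled.** There is no formal testing, the restriction of TTNT is stated, the proportion switching is reported in the same section, and the preamble to Section 8 lets the SAP change the method. This lowers the severity. It does not make a switcher-only summary an estimate of TTNT in treated participants, and the proportion switching does not correct its timing.
- **DoT need not be short.** A reader might infer that both durations are certainly biased short. The documents do not support that for DoT. Under the Section 3 definition everyone has observed exposure, and entering it leaves the median nearly intact. What is shown is a missing rule, with a median that is clearly short only if ongoing participants are left out.
- **Comparability with the earlier trial.** A reader might infer that neither result could be set beside that trial's medians. No TTNT median is quoted, and Section 2.3 does not say how its DoT medians were estimated, so this is not shown.
- **Dose reduction and treatment duration.** The synopsis says "It will also assess the impact of dose modifications on treatment duration", and Section 8.4.3.3 lists "The DoT in regard to dose reduction". A reader might infer a comparison of participants ever and never reduced, which would favour the reduced group simply because longer treatment leaves more time for a reduction. The protocol states no such grouping and leaves the details to the SAP, so this is not a finding.
- **Kaplan-Meier is not a complete cure for TTNT.** This stands. Next-therapy dates have no planned collection point for stops in months 15–18 or for switches after the follow-up visit, and several places tie that visit to having already switched. The remedy therefore needs a caveat and, where possible, more complete recording.

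**Conclusion.** The point holds for TTNT as a fixed analysis rule that gives a biased result. The direction is certain. The size is model-based: roughly 17–38% short on the median in the mixture simulation, and more if the true median is near 18 months. For DoT, the protocol leaves the contribution of about 10% (epNET) and 22% (pNET) of participants undefined at the quoted medians. The effect runs from almost none on the median (ongoing entered as 18 months, no dropout) to a fall of 0.8 or 2.4 months (ongoing dropped), while the mean is short either way. These sizes rest on exponential times, an 18-month window counted from first dose, no separate death process and, in the simulations, the assumed gap to next therapy. Should-fix: the endpoints are secondary and descriptive, and the correction is simple.

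**What to change.** Reword Section 8.4.3.2 and the matching synopsis text so that DoT and TTNT are estimated on the FAS by Kaplan-Meier, with medians, quartiles and 95% CIs where reached.

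- **DoT:** censor ongoing treatment at the last date known on cabozantinib, and use one definition in Sections 3 and 6.1.2.
- **TTNT:** censor participants without a next therapy at last contact. State how death before a next therapy is handled: as an event, or as a competing event with cumulative incidence. Keep the switcher-only summary as a supplement labelled as conditional on switching.
- **Caveat and data:** state that censoring after cabozantinib is stopped may be informative and may overstate TTNT. Where routine records allow, record the start date of the next therapy up to Month 18, including for stops in months 15–18.

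The DoT change costs wording only, since start and stop dates are already collected. The TTNT change adds one eCRF date taken from existing records, with no extra procedure for participants. If that date cannot be obtained, Kaplan-Meier with the caveat is still preferable to the switcher-only summary as the main result, but it should be read as possibly too long. The wording should be settled before IA2.
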